The total planned study duration (screening to EOS) for each participant will be up to 7 weeks. This includes a screening period of up to 4 weeks (ie, within 28 days prior to dosing on Day 1) and a treatment period of at least 1 week (Days 1 to 8) until at least one discharge criterion is met, up to maximum of 3 weeks (Days 1 to 22). Participants who terminate the study early will be asked to return to the study site 7±2 days after dosing for follow-up procedures, and to determine if any AE has occurred since the last study visit.

Data Monitoring/Other Committee: No

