8.4 Adverse Events, Serious Adverse Events, and Other Safety Reporting

The definitions of AEs and SAEs are provided below, as are criteria for assessment of AE/SAE intensity and causality.

The Investigator and any qualified designees are responsible for detecting, documenting, and recording events that meet the definition of an AE or SAE and remain responsible for following up AEs that are serious, considered related to the study drug or study procedures or that caused the participant to withdraw from the study (see Section 7).

AE Definition

- An AE is any untoward medical occurrence in a patient or clinical study participant, temporally associated with the use of study drug, whether or not considered related to the study drug.
- NOTE: An AE can therefore be any unfavourable and unintended sign (including an abnormal laboratory finding), symptom, or disease (new or exacerbated) temporally associated with the use of study drug.

Events Meeting the AE Definition

- Any abnormal laboratory test results (haematology, clinical chemistry, coagulation, or urinalysis) or other safety assessments (eg, ECG, radiological scans, vital signs measurements), including those that worsen from screening (signing of the ICF), considered clinically significant in the medical and scientific judgement of the Investigator (ie, not related to progression of underlying disease, or more severe than expected for the participant's condition).
- Exacerbation of a chronic or intermittent pre-existing condition including either an increase in frequency and/or intensity of the condition.
- New conditions detected or diagnosed after study drug administration even though it may have been present before signing the ICF.
- Signs, symptoms, or the clinical sequelae of a suspected drug-drug interaction or that resulted in additional intervention (eg, concomitant medication, surgery).
- Signs, symptoms, or the clinical sequelae of a suspected overdose of either study drug or a concomitant medication. Overdose per se will not be reported as an AE/SAE unless it is an intentional overdose taken with possible suicidal/self-harming intent. Such overdoses should be reported regardless of sequelae.

Events not meeting the AE definition

- Any abnormal laboratory findings or other abnormal safety findings that are not considered to be clinically significant by the Investigator.
- Medical or surgical procedure (eg, endoscopy, appendectomy): the condition that leads to the procedure is the AE.

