 - Examples of such events include invasive or malignant cancers, intensive treatment in an emergency room or at home for allergic bronchospasm, blood dyscrasias or convulsions that do not result in hospitalisation, or development of study drug dependency or study drug abuse.

An SAE must be reported for participants with ALT or AST \geq 3 × ULN and bilirubin \geq 2 × ULN (>35% direct).

Definition of SUSAR

A SUSAR is an SAE with at least a reasonable possibility of being related to the study drug (ie, the relationship cannot be ruled out), the nature or severity of which is not consistent with the applicable product information (eg, IB for an unapproved investigational product or package insert/summary of product characteristics for an approved product).

Assessment of Intensity

The Investigator will assess intensity for each AE and SAE reported during the study and assign it to 1 of the following categories:

- Mild: A type of AE that is usually transient and may require only minimal treatment or therapeutic intervention. The event does not generally interfere with usual activities of daily living.
- Moderate: A type of AE that is usually alleviated with additional specific therapeutic intervention. The event interferes with usual activities of daily living, causing discomfort but poses no significant or permanent risk of harm to the research participant.
- Severe: A type of AE that interrupts usual activities of daily living, or significantly affects clinical status, or may require intensive therapeutic intervention.

Assessment of Toxicitiy

Separately, the toxicity of AEs will be graded in accordance with the FDA Guidance for Industry: Toxicity Grading Scale for Healthy Adult and Adolescent Volunteers Enrolled in Preventive Vaccine Clinical Trials (Section 10.5). Any event not falling under one of the specific categories listed will be graded as a "Systemic Illness".

For events that occur after signing of the ICF, the maximum intensity, toxicity, and seriousness should be reflected in the event record.

Assessment of Causality

- The Investigator is obligated to assess the relationship between study drug and each occurrence of each AE/SAE. The relationship of each AE to study drug will be assessed using the following categories:

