8.4.1 Time Period and Frequency for Collecting AE and SAE Information

All AEs and SAEs will be collected from ICF signature until discharge on Day 8 (up to Day 22). Any ongoing AEs at the time of discharge will be appropriately followed-up until resolution or 14 days (±2 days) after discharge or early termination. Any ongoing SAEs will be followed-up until resolution or lost to follow-up.

All SAEs will be recorded and reported to Indivior or designee immediately and under no circumstance should this exceed 24 hours from first becoming aware of the event, as indicated in Section 8.4.3. The Investigator will submit any updated SAE data to Indivior within 24 hours of it being available.

Investigators are not obligated to actively seek AEs or SAEs after conclusion of the study participation. However, if the Investigator learns of any SAE, including a death, at any time after a participant has been discharged from the study, and the Investigator considers the event to be reasonably related to the study drug or study participation, the Investigator must promptly notify Indivior.

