9.3.3 Secondary Endpoints Analysis

TEAEs will be defined as AEs that start at or after dosing of study drug and will be summarised by Medical Dictionary for Regulatory Activities system organ class and preferred term. TEAEs will be summarised for the Safety Analysis Set.

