5.6.2. Adverse Events

A TEAE starts at or after study drug dosing. AEs will be coded to a System Organ Class (SOC) and Preferred Term (PT) using Medical Dictionary for Regulatory Activities (MedDRA). Additional details of the coding process, including the current version of the dictionary, are described in the Data Management Plan.

All AEs will be listed for individual subjects. Listings will include SOC, PT, and reported term; onset date and time, end date, and duration; treatment-emergence, severity, toxicity grade, seriousness and seriousness criteria; relationship to study drug; whether concomitant treatment was given; outcome; and whether the AE resulted in study discontinuation. Duration (days) is calculated as the AE end date – the AE onset date +1; for ongoing AEs, the date of end of study participation will be used as the end date. Duration will be missing if either the start or end date is partially or completely missing. TESAEs, TEAEs leading to study discontinuation, and fatal TEAEs will be listed separately.

The incidence and number of all TEAEs, TESAEs, study drug-related TEAEs and study drug-related TESAEs, severe TEAEs, TEAEs with grade 3 or higher toxicity grade, TEAEs leading to study discontinuation, and fatal TEAEs will be presented in an overall summary table.

TEAEs, TESAEs, study drug-related TEAEs and study drug-related TESAEs will be summarized by MedDRA SOC and PT, each in descending order of frequency among all subjects (then alphabetically in case of ties). TEAEs will also be summarized by maximum severity and by maximum toxicity within SOC and PT. If an AE is reported more than once by a subject within a SOC and/or PT, the maximum reported level of severity/toxicity will be used at each level of summation in the severity/toxicity summary tables. Incidence and number of TEAEs will also be summarized by PT only (ie, not SOC), sorted by descending frequency among all subjects.

Non-TEAEs are defined as AEs that started before study drug dosing. Non-TEAEs will be summarized for the Safety Analysis Set.

See Section 6.6.2 (Appendix 6) for details on handling of missing AE information.

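### TEAEs are defined by onset alone, so an AE already open at dosing that worsens afterwards is left, as the plan is written, outside the TEAE-based secondary safety endpoint

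*SAP*

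**What the plan says.** Both documents classify by onset. Protocol 9.3.3: "TEAEs will be defined as AEs that start at or after dosing of study drug". SAP 5.6.2: "A TEAE starts at or after study drug dosing". The complement is explicit: "Non-TEAEs are defined as AEs that started before study drug dosing", and "Non-TEAEs will be summarized for the Safety Analysis Set".

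The secondary endpoint (Protocol section 3, SAP 5.4.1) is built on TEAEs only. In SAP 5.6.2 the SOC and PT tables, the maximum-severity and maximum-toxicity tables and the rows of the overall summary (serious, related, severe, grade 3 or higher, leading to discontinuation, fatal) are all restricted to treatment-emergent events.

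AE collection begins at ICF signature (Protocol 8.4.1), and screening may last up to 28 days before dosing (Protocol 1.1). On what is recorded, Protocol 8.4 says: "For events that occur after signing of the ICF, the maximum intensity, toxicity, and seriousness should be reflected in the event record". The same section counts as an AE: "Exacerbation of a chronic or intermittent pre-existing condition including either an increase in frequency and/or intensity of the condition".

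**The concern.** In a single-dose study, a complaint that is mild before dosing and clearly worse afterwards is one of the patterns in which a drug effect could show. A rule based only on onset date cannot pick it up. The recording rule adds to the difficulty: if the existing record is updated to the worst level, a post-dose grade sits under a pre-dose onset and the record is then classed as not treatment-emergent.

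At stake is the completeness of the descriptive secondary safety endpoint. The mass balance and PK results are not affected, and no hypothesis is tested. The possible error runs one way only: the rule can remove events from the TEAE tables or leave a man in a milder category, but it cannot add events.

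**Working it through.** The plan states no figure on this point, so there is none to reproduce. The check sets the rules side by side and then gives the weight of one case.

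**Step 1. Is there a worsening clause anywhere?**

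| Place | What decides treatment emergence | Uses change after dosing? |
|---|---|---|
| Protocol 9.3.3 | AE onset relative to dosing | No |
| SAP 5.6.2, TEAE | AE onset relative to dosing | No |
| SAP 5.6.2, non-TEAE | AE onset before dosing | No |
| SAP 6.6.2, missing dates | Known parts of the start date, and whether the AE ended before dosing | No |

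**Step 2. Does an open AE get a new onset when it worsens?** Protocol 8.4 has the worst level reflected in the event record for events after consent. Protocol 8.4.3.2 sends new or updated information to the documents already submitted. Neither says that worsening opens a second record. The exacerbation bullet makes worsening of a pre-existing condition an AE, but it gives no record or onset rule for an AE that began between consent and dosing.

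**Step 3. Apply the rules to one case.** Take an AE with onset on Day -1, mild before dosing and severe after it.

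- Record, if the existing one is updated: onset Day -1, maximum severity severe.
- Classification: non-TEAE.
- Absent from: all TEAE counts, the severe row, the grade 3 or higher row if graded so, the related row if judged related, and the TESAE row and listing if serious.
- Present in: the all-AE listing and the non-TEAE summary. The listing fields in SAP 5.6.2 include onset, end date, severity, grade and seriousness, but no date of worsening. A reader therefore cannot tell whether the worst level came before or after dosing.

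**Step 4. Weight of one man.** The denominator is everyone dosed: about 7 (Protocol 9.5, SAP section 3).

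- Shift in a row if he has no other event in it: 1/7 = 0.143, or 14.3 percentage points. If only 6 were dosed: 1/6 = 0.167, or 16.7 points.
- In the example, the severe-TEAE row reads 0/7 under the stated rule and 1/7 if worsening counts.
- If he already has another event in that row, its incidence does not move.

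**Step 5. How often?** The documents give no rate. Purely as an assumption, let p be the chance that a dosed man has such an AE, independently of the others. The chance of at least one case is 1 - (1 - p)^n.

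| Assumed p | n = 7 | n = 6 |
|---|---|---|
| 2% | 1 - 0.98^7 = 13.2% | 11.4% |
| 5% | 1 - 0.95^7 = 30.2% | 26.5% |
| 10% | 1 - 0.90^7 = 52.2% | 46.9% |

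These values of p illustrate a range and are not estimates.

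**The case against.** The best reply is that the documents leave room for the event to be captured. The exacerbation bullet is not limited to medical history, and the AE definition in Protocol 8.4 covers signs and symptoms that are new or exacerbated. An investigator could enter a worsened headache as a fresh AE with post-dose onset. The CRF completion guidelines (Protocol 10.1.6), which are not among these documents, may require that. Protocol 8.4 also says that clinically significant screening laboratory findings are not AEs, and that clinically significant safety findings which worsen from screening are. Some laboratory, vital-sign and ECG changes would therefore get a post-dose onset anyway.

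The event is also not hidden. Every AE is listed by participant, non-TEAEs are summarised, and SAEs go to the sponsor within 24 hours whatever their classification. With about 7 men, each line can be read.

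Much of this stands, and it limits the point. It does not close the gap for a symptom already recorded as an AE before dosing, because no text gives it a new onset, and the listing carries no date that would let a reader reclassify it.

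A reader might infer more than the documents support:

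- **That the protocol prescribes one record per event.** This is an inference from the singular event record in 8.4 and the follow-up text in 8.4.3.2; it is not stated.
- **That pre-dose complaints are likely because of fasting and caffeine abstinence.** Both restrictions are in the protocol, but no frequency of complaints is given. A pre-dose complaint is also not the same as post-dose worsening.
- **That 14.3 points is an expected bias.** It is the weight of one man, and it applies only under the condition in Step 4.

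**Conclusion.** The point holds as a defect in a stated definition. Applied literally, the onset-only rule leaves post-dose worsening of an already open AE out of the secondary endpoint and its serious, related, severe and high-grade summaries. The all-AE listing does not repair this.

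The conclusion rests on one reading that the documents favour but do not state: that worsening updates the existing record. If the site instead opens a new record, the present definition would already capture the event, but the plan should say so.

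The size is modest. The case is probably rare in healthy men given one dose, and no rate is available. Each case can move a row by up to 14.3 points at n = 7, always towards fewer or milder TEAEs. Elsewhere SAP 6.6.2 resolves doubt the cautious way: unresolved severity is taken as severe and unresolved relationship as related. The onset-only rule is out of step with that.

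**What to change.** Use one mechanism and keep one record per episode.

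1. In SAP 5.6.2, define a TEAE as an AE that begins at or after dosing, or one that begins before dosing and, at or after dosing, rises in intensity or toxicity grade or becomes serious. State that the rise is measured against the highest level reached before dosing, so that the level that triggers reclassification is a post-dose one.
2. Define a non-TEAE as an AE that began before dosing and did not worsen after it.
3. Capture the date and time of worsening on the existing record, and show them in the all-AE listing.
4. Log the departure from Protocol 9.3.3 in SAP Appendix 2. SAP section 1 lets the SAP supersede the protocol's statistical section and calls for a protocol amendment only for major changes to the primary endpoint.

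Do not also enter the worsening as a new AE. With both rules in force, one episode could count twice in the number of TEAEs, and the new-record rule would have to be reconciled with Protocol 8.4. Keeping the existing record leaves 8.4 as it is.

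The cost is a short SAP revision, one CRF date field or completion instruction, and a reported TEAE count that may be slightly higher.

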5.6.3. Additional Safety Assessments

5.7. Other Analyses

5.7.1. Demographics and Anthropometrics

Demographics and anthropometrics will be summarized separately for the safety and PK analysis sets, if different. Parameters to be summarized will include age, race, ethnicity, and height/weight/body mass index.

5.7.2. Medical History

Relevant medical history will be coded using MedDRA (refer to the Data Management Plan) and will be listed for the safety analysis set.

5.7.3. Prior and Concomitant Medications and Therapies

Medications and therapies will be collected from screening through EOS and will be coded using Anatomical Therapeutic Chemical (ATC) classification codes via the World Health Organization Drug Dictionary (WHO-DD). Additional details of the coding process, including the current version of the dictionary, are described in the Data Management Plan. Prior medications and therapies ended before dosing or were taken by subjects who were never dosed. All other medications and therapies will be considered concomitant.

Prior and concomitant medications and therapies will be summarized separately for the safety analysis set. The summary of incidence (number and percentage of subjects reporting the medication or therapy at least once) will be sorted alphabetically by therapeutic class (ATC level 2) and standardized medication/therapy name.

See Section 6.6.3 (Appendix 6) for details on handling missing information on medications and therapies.

5.7.4. Protocol Deviations

Protocol deviations will be identified and documented prior to database lock and will be summarized by category (eg, prohibited medication, out-of-window assessment) and type (eg, important, not important), per the Protocol Deviation Assessment Tool for the study, for the safety analysis set. Deviations that occur in subjects who were not in the safety analysis set, if any, will be summarized separately. All protocol deviations will be listed.

5.8. Interim Analyses

Not applicable.

6. SUPPORTING DOCUMENTATION

percent of administered dose excreted/recovered within a given collection intervalAnalysis Data Modelabsorption, distribution, metabolism and excretionadverse eventamount of total radioactivity excreted/recovered within a given collection intervalAnatomic Therapeutic Chemical
Analysis Data Modelabsorption, distribution, metabolism and excretionadverse eventamount of total radioactivity excreted/recovered within a givencollection interval
absorption, distribution, metabolism and excretionadverse eventamount of total radioactivity excreted/recovered within a givencollection interval
adverse event amount of total radioactivity excreted/recovered within a given collection interval
adverse event amount of total radioactivity excreted/recovered within a given collection interval
collection interval
collection interval
Anatomic Therapeutic Chemical
area under the curve
area under the curve from 0 to infinity
area under the curve extrapolated as a percentage of the total $AUC_{0-\infty}$
area under the curve from dosing to the last measured concentration
below limit of quantitation
maximum plasma concentration
apparent total clearance of drug from plasma after oral administration
renal clearance
Case Report Form
clinical study report
cumulative percent of dose excreted/recovered
cumulative amount of total radioactivity excreted/recovered
coefficient of variation
end of study
high-performance liquid chromatography
terminal elimination rate constant
microcurie
Medical Dictionary for Regulatory Activities
metabolic ratio of $AUC_{0-\infty}$
metabolic ratio of C _{max}
pharmacokinetic(s)
Preferred Term
ratio of unlabeled plasma drug AUC _{last} to plasma TRA AUC _{last}
ratio of unlabeled plasma drug C_{max} to plasma TRA C_{max}
statistical analysis plan
standard deviation
Study Data Tabulation Model
System Organ Class
apparent terminal half-life
time of maximum plasma concentration
treatment-emergent adverse event
tables, figures, and listings
total radioactivity
apparent volume of distribution during the terminal elimination phase
after oral administration
World Health Organization Drug Dictionary

6.1. Appendix 1: List of Abbreviations

6.2. Appendix 2: Changes to Protocol-Planned Analyses

The following are changes from the protocol that are in the SAP:

6.3. Appendix 3: Definition and Use of Visit Windows in Reporting

No windowing will be used for summaries. Analysis visits will be visits denoted in the Case Report Form (CRF). An early termination visit will be counted as a scheduled visit if it occurs on a scheduled visit study day; otherwise, it will be counted as an unscheduled visit. If a participant has more than 1 assessment for a given visit, the most recent non-missing assessment will be used for summaries.

6.4. Appendix 4: Endpoint Derivations

6.4.1. Mass Balance and PK Endpoints

Individual plasma, and whole blood, urine, and feces samples are collected according to the schedules outlined in Section 10.4 of the protocol.

6.4.1.1. Urine and Feces Mass Balance and PK Parameters

TRA recovery and the percent of the radioactive dose excreted in the urine and feces from pre-dose to at least 168 hours, as applicable, will be assessed on a per participant basis. Mass balance will be calculated as a sum of the percent of the TRA recovered in urine and feces relative to the administered radioactive dose. If emesis occurs, the calculation of mass balance may take into account any radioactivity recovered in the vomitus as appropriate.

Urine, feces, and urine + feces parameters to be calculated are shown in Table 6. Additional parameters may be calculated if required.

Parameter	Definition
Ae _{t1-t2}	Amount of total radioactivity excreted/recovered within a given collection interval
CumAe	Cumulative amount of total radioactivity excreted/recovered
%DoseAe	Percent of administered dose excreted/recovered within a given collection interval
Cum%Dose	Cumulative percent of dose excreted/recovered
CLr	Renal clearance. $CL_r = CumAeAe_{t1-t2}/AUC$, where both CumAeAe_{t1-t2} and AUC are determined over matched time interval (urine only)

 Table 5
 Mass Balance and PK Parameters : TRA – Urine, Feces, and Urine + Feces

6.4.1.2. Plasma and Whole Blood PK Parameters

Plasma and whole blood PK parameters to be calculated are shown in Table 5. Additional parameters may be calculated if required.

Table 6PK Parameters: TRA, Unlabeled Plasma IDV184001, and Unlabeled Plasma
M12 – Plasma and Whole Blood

Parameter	Definition
C _{max}	Maximum observed concentration
T _{max}	Time of maximum observed concentration
AUC _{last}	Area under the concentration-time curve from time 0 to the time of the last quantifiable concentration; calculated using the linear trapezoidal rule

Parameter	Definition
AUC _{0-∞}	Area under the concentration-time curve from time 0 extrapolated to infinite time
AUC _{extrap(%)}	Percent of the area under the concentration-time curve due to extrapolation
λz	Terminal phase rate constant
t _{1/2}	Apparent terminal half-life
CL/F	Apparent total clearance after oral (extravascular) administration, calculated as Dose/ AUC _{0-∞} (parent only)
V _z /F	Apparent volume of distribution during the terminal elimination phase after oral (extravascular) administration, calculated as Dose/(AUC _{0-∞} × λ_z) (parent only)
MRAUC _{0-∞}	Metabolic ratio of the metabolite $AUC_{0-\infty}$ to the parent $AUC_{0-\infty}$
MRC _{max}	Metabolic ratio of the metabolite C_{max} to the parent C_{max}
RAUC _{last (plasma)}	Ratio of unlabeled plasma drug AUC _{last} to plasma TRA AUC _{last}
RC _{max (plasma)}	Ratio of unlabeled plasma drug C _{max} to plasma TRA C _{max}

To calculate the slope of the terminal phase (λ_z) , the following acceptance criteria will be used:

- $Rsq \ge 0.80$
- Minimum of three time points in the terminal phase (not including C_{max})
- AUC_{0-inf} will be calculated if the percentage of AUC extrapolation (AUC_{extrap(%)}) is <=20%

Actual sampling times will be used in PK parameter calculations.

